3.2 Exclusion criteria

Patients should not enter the study if any of the following exclusion criteria are fulfilled:

1. Previous randomisation and treatment in the present study
2. Treatment with any of the following:
 - Pre-operative or post-operative or planned radiation therapy for the current lung cancer
 - Pre-operative (neo-adjuvant) platinum based or other chemotherapy
 - Any prior anticancer therapy, including investigational therapy, for treatment of NSCLC other than standard platinum based doublet post-operative adjuvant chemotherapy
 - Prior treatment with neoadjuvant or adjuvant EGFR-TKI
 - Major surgery (including primary tumour surgery, excluding placement of vascular access) within 4 weeks of the first dose of study drug
 - Patients currently receiving (or unable to stop use prior to receiving the first dose of study treatment) medications or herbal supplements known to be potent inducers of CYP3A4 (at least 3 weeks prior).
 - Treatment with an investigational drug within five half-lives of the compound or any of its related material, if known.

3. Patients who have had only segmentectomies or wedge resections
4. History of other malignancies, except: adequately treated non-melanoma skin cancer, curatively treated in-situ cancer, or other solid tumours curatively treated with no evidence of disease for > 5 years following the end of treatment and which, in the opinion of the treating physician, do not have a substantial risk of recurrence of the prior malignancy.
5. Any unresolved toxicities from prior therapy greater than CTCAE Grade 1 at the time of starting study treatment with the exception of alopecia and Grade 2, prior platinum-therapy related neuropathy.
6. Any evidence of severe or uncontrolled systemic diseases, including uncontrolled hypertension and active bleeding diatheses, which in the Investigator's opinion makes it undesirable for the patient to participate in the trial or which would jeopardise compliance with the protocol; or active infection including hepatitis B, hepatitis C and human immunodeficiency virus (HIV). Active infection will include any patients receiving intravenous treatment for infection; active hepatitis B infection will, at a minimum, include all patients who are hepatitis B surface antigen positive (HbsAg positive) based on serology assessment. Screening for chronic conditions is not required.
7. Refractory nausea and vomiting, chronic gastrointestinal diseases, inability to swallow the formulated product, or previous significant bowel resection that would preclude adequate absorption of AZD9291.
8. Any of the following cardiac criteria:
 - Mean resting corrected QT interval (QTc) >470 msec, obtained from 3 ECGs, using the screening clinic ECG machine-derived QTcF value.
 - Any clinically important abnormalities in rhythm, conduction, or morphology of resting ECG, e.g., complete left bundle branch block, third-degree heart block, second-degree heart block.
 - Any factors that increase the risk of QTc prolongation or risk of arrhythmic events such as heart failure, hypokalaemia, congenital long QT syndrome, family history of long QT syndrome, or unexplained sudden death under 40 years of age in first-degree relatives or any concomitant medication known to prolong the QT interval.
9. Past medical history of ILD, drug-induced ILD, radiation pneumonitis which required steroid treatment, or any evidence of clinically active ILD.
10. Inadequate bone marrow reserve or organ function as demonstrated by any of the following laboratory values:
 - Absolute neutrophil count <1.5 x 10⁹/L.
 - Platelet count <100 x 10⁹/L.
 - Haemoglobin <90 g/L.
 - Alanine aminotransferase (ALT) >2.5x the upper limit of normal (ULN).
 - Aspartate aminotransferase (AST) >2.5xULN.

- Total bilirubin $>1.5 \times \text{ULN}$ or $>3 \times \text{ULN}$ in the presence of documented Gilbert's Syndrome (unconjugated hyperbilirubinaemia).
- Creatinine $>1.5 \times \text{ULN}$ concurrent with creatinine clearance $<50 \text{ mL/min}$ (measured or calculated by Cockcroft and Gault equation); confirmation of creatinine clearance is only required when creatinine is $>1.5 \times \text{ULN}$.

11. Women who are breast feeding.
12. History of hypersensitivity to active or inactive excipients of AZD9291 or drugs with a similar chemical structure or class to AZD9291.
13. Judgment by the Investigator that the patient should not participate in the study if the patient is unlikely to comply with study procedures, restrictions, and requirements.
14. Involvement in the planning and/or conduct of the study (applies to both AstraZeneca representative and/or staff at the study site).

In addition, the following are considered criteria for exclusion from the exploratory genetic research only:

1. Prior allogeneic bone marrow transplant.
2. Non-leukocyte depleted whole blood transfusion within 120 days of genetic sample collection.

Procedures for withdrawal of incorrectly enrolled subjects see Section 3.5.

3.3 Eligibility for post-recurrence open-label osimertinib

In addition to meeting inclusion/ exclusion criteria listed in Sections 3.1 and 3.2, patients who receive open-label osimertinib will also have to fulfil the following criteria.

1. Patients must have locally advanced recurrence not amenable to definitive treatment and/or curative approach; or distant metastatic recurrence (recurrence stage IV per AJCC 7th edition). Such recurrence must be confirmed with unequivocal imaging findings or biopsy confirmation.
2. Most recent haematology panel, chemistry panel, ECG and LVEF assessments will have been completed within 4 weeks prior to the start of open-label osimertinib treatment and do not show any clinically significant findings.
3. Patient deemed likely to benefit from and tolerate open-label osimertinib per accepted clinical guidelines and regional package insert.
4. Patient will have received appropriate guidance from the treating Investigator regarding post-recurrence treatment options, and will have signed the most recent Informed Consent Form.
5. Patients must not receive any other systemic anti-cancer therapies (other than osimertinib) between the discontinuation of study treatment and the start of treatment with open-label osimertinib.

6. Past medical history of ILD/pneumonitis, drug-induced ILD/pneumonitis, radiation pneumonitis which required steroid treatment, or any evidence of clinically active ILD/pneumonitis.
7. Patients with recurrence eligible for open-label osimertinib should have completed imaging modalities for chest, abdomen (including liver and adrenal glands) and brain with contrast at the time of recurrence.
8. Patients with any unresolved toxicity CTCAE Grade 3 or higher from the prior study treatment should be excluded.

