1.5 Benefit/risk and ethical assessment for conducting the ADAURA study

Although there can be no certainty of clinical benefit to patients, success of other targeted agents in the adjuvant setting with or without chemotherapy, non-clinical characteristics of AZD9291, the preliminary data of EGFR-TKIs in this setting, the preliminary clinical efficacy and safety data with AZD9291 in the ongoing phase I trial (D5160C00001) all support the notion that EGFR mutation inhibition may be a valid strategy for the adjuvant treatment of completely resected NSCLC tumours which are driven via this pathway. Specifically, the safety profile of AZD9291 in the ongoing phase I trial extended to phase II and ongoing clinical program was already favourable at the time of study start-up with the majority of toxicities being low grade EGFR related adverse events (Common Terminology Criteria for Adverse Event [CTCAE] Grade 1 or 2), i.e., diarrhoea and skin rash.

Based on the information available at the time of IDMC7, AZD9291 remains generally well tolerated in the metastatic setting. The majority of adverse reactions are of Grade 1 or 2 severity, and the most frequent reactions are typical EGFR-TKI side effects including rash and diarrhoea. Interstitial lung disease (ILD) or ILD-like adverse drug reactions (e.g., pneumonitis) are commonly reported (3.9% of patients in Phase I-III studies), and occasionally fatal (0.4%) for patients receiving AZD9291. Details of important identified and potential risk for AZD9291 can be found in the Investigators' brochure.

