All trials of AZD9291 exclude patients with clinically significant toxicities related to prior treatments in addition to specifically excluding patients with a history of ILD or clinically active ILD as this is an uncommon but well documented EGFR-related toxicity. Patients requiring radiotherapy will be excluded from participation due to the potential risk of radiation induced pneumonitis. In the pre-clinical studies, the principal target organ findings were consistent with inhibition of wild type EGFR (atrophic, inflammatory and degenerative changes in the skin, cornea, gastrointestinal tract and female reproductive tract). Other target organ findings of potential clinical relevance were seen in the male reproductive tract and male mammary gland. All patients will be assessed for possible known EGFR-related toxicities and detailed information on the management of EGFR-related gastrointestinal, dermatological, and ophthalmologic toxicities is being provided for all AZD9291 studies.

It is therefore, reasonable to evaluate the oral administration of AZD9291 in comparison to placebo as adjuvant therapy in preventing or delaying the recurrence of disease in EGFR⁺ NSCLC patients who have undergone complete surgical resection and standard of care chemotherapy where applicable.

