3.10 Discontinuation of investigational product or open-label osimertinib

Patients may be discontinued from IP or open-label osimertinib in the following situations:

- Patient decision. The patient is at any time free to discontinue his/her participation in the study, without prejudice
- Adverse event
- Pregnancy
- Severe non-compliance with the study protocol as judged by the Investigator and/or AstraZeneca representative
- Patients who are incorrectly initiated on IP
- Disease recurrence (for select patients who might have the option of open-label osimertinib upon recurrence, please also see Section 3.3)
- Subsequent progression (for patients who started open-label osimertinib upon recurrence) or until a time when the investigator considers that they are no longer deriving clinical benefit.
- Patients experiencing ILD/pneumonitis, or QTc prolongation with signs/symptoms of serious arrhythmia will not be permitted to restart study treatment.
- Patient completes the treatment period of 3 years (156 weeks) as planned (not applicable to patients receiving open-label osimertinib upon recurrence)

3.10.1 Procedures for discontinuation of a subject from investigational product or open-label osimertinib

At any time, patients are free to discontinue IP without prejudice to further treatment. A patient that decides to discontinue IP will always be asked about the reason(s) for discontinuation of IP and the presence of any AEs. The patient or representative will return all unused study drugs. This will also apply to patients on open-label osimertinib.

As long as the patient does not withdraw consent for the study, visits will be continued according to study plan. Treatment discontinuation visit will be conducted as soon as possible after the patient received the last dose of investigational product and safety follow up will be performed 28 days (+7 days) after drug discontinuation.

“Follow up until disease recurrence” visits should continue according to study plan if the patient discontinues study treatment prior to disease recurrence. Radiological assessments will be performed at 12 weeks, 24 weeks and then every 24 weeks up to 5 years and yearly thereafter (+/- 7 days) (relative to randomisation) until disease recurrence. Serious adverse events considered related to the study procedures must be collected while patients are followed up for disease recurrence.

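### Protocol 3.3 item 6 lists ILD/pneumonitis, without a negation, among criteria that open-label osimertinib patients must fulfil; as a lesser point, 6.3.1, 6.9.1 and 7.3.3 name different sources for managing their dose

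*Protocol*

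**What the plan says.** **Eligibility.** Protocol 3.3 first requires the criteria of 3.1 and 3.2 to be met. It then says that "patients who receive open-label osimertinib will also have to fulfil the following criteria", and eight numbered items follow. Section 4.4 repeats the obligation. Item 6 is "Past medical history of ILD/pneumonitis, drug-induced ILD/pneumonitis, radiation pneumonitis which required steroid treatment, or any evidence of clinically active ILD/pneumonitis". Two other items that keep patients out say so themselves. Item 5 begins "Patients must not receive any other systemic anti-cancer therapies (other than osimertinib) between the discontinuation of study treatment", and item 8 reads "Patients with any unresolved toxicity CTCAE Grade 3 or higher from the prior study treatment should be excluded".

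Elsewhere, ILD history is a ground for keeping patients out:

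- Protocol 3.2, exclusion 9: "Past medical history of ILD, drug-induced ILD, radiation pneumonitis which required steroid treatment, or any evidence of clinically active ILD". SAP Table 2 repeats this as an important deviation under the exclusion criteria.
- Protocol 1.5 describes all trials of the drug as "specifically excluding patients with a history of ILD or clinically active ILD as this is an uncommon but well documented EGFR-related toxicity".
- Protocol 3.10, on discontinuation: "Patients experiencing ILD/pneumonitis, or QTc prolongation with signs/symptoms of serious arrhythmia will not be permitted to restart study treatment".
- Protocol 6.9.6 has study drug permanently discontinued once ILD/pneumonitis is confirmed.

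**Dose modification.** Protocol 6.9.1 sends open-label patients to the approved local label and sets no time limit. Protocol 6.3.1 tells their investigators to follow the package instructions. Protocol 7.3.3, for open-label patients after the final OS analysis and during the extension, says that protocol criteria for dose modification and stopping apply. It adds that dose changes should in general follow the protocol's approach.

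**The concern.** Section 3.3 is an operative list. Section 4.4 allows open-label treatment to start at any time before the data cut-off for the long-term OS analysis, so sites may still be using it. A criterion that says the opposite of what related sections say leaves each site to work out the intended sense for itself.

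The subject is not trivial. Section 1.5 says that ILD or ILD-like reactions "are commonly reported (3.9% of patients in Phase I-III studies), and occasionally fatal (0.4%) for patients receiving AZD9291". Section 6.3.1 singles out ILD/pneumonitis for collection in open-label patients even when the event is not serious.

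On dosing, a site treating a patient in the extension cannot tell from the text alone whether the label or the protocol governs.

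**Working it through.** No formula applies and the plan gives no figure to reproduce. The check is a comparison of current protocol text; nothing rests on the amendment log.

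**1. Where the item 6 wording comes from.** Delete /pneumonitis from item 6 (three occurrences) and the remaining 20 words are identical to the 20 words of exclusion 9. What differs is the lead-in. In 3.2 the list is of things that keep a patient out; in 3.3 it is of things a patient has to fulfil.

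**2. Whether the list signals an exclusion sense.**

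| Item in 3.3 | Own negation? | Sense as worded |
|---|---|---|
| 5, intervening systemic therapy | yes | keeps out |
| 6, ILD/pneumonitis | no | required |
| 7, imaging at recurrence | none needed | required |
| 8, unresolved Grade 3 or higher toxicity | yes | keeps out |

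Item 7, directly after item 6, is a genuine requirement. A lost subheading above item 6 turning the rest of the list into exclusions would therefore not explain the text, because it would reverse item 7.

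**3. What follows depends on when 3.2 applies.** The two readings below are alternatives and cannot both be used at once.

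- *3.2 is applied again at open-label start.* The lead-in of 3.3 and section 4.4 support this. A patient with ILD then meets item 6 and fails exclusion 9; a patient without it passes exclusion 9 and fails item 6. Apart from any pneumonitis that a site would not class as ILD, nobody satisfies both. The contradiction is direct.
- *3.2 applies at study entry only.* Exclusion 1, on earlier randomisation and treatment in this study, supports this, since taken literally at recurrence it would bar every candidate. Exclusion 9 then does not reach ILD first seen after randomisation, and there is no direct contradiction with it. Item 6 becomes the only criterion in 3.3 that names ILD, and as worded it points the opposite way from the other places that do. Partial protection remains: item 3 asks that the patient be likely to tolerate the drug under guidelines and the regional insert, item 8 removes unresolved Grade 3 or higher toxicity, and 6.9.6 ends study drug after confirmed ILD.

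Under either reading item 6 is defective as worded.

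**4. Whether 3.10 settles it.** Its heading covers both the investigational product and open-label osimertinib. The ILD sentence, however, bars restarting *study treatment*, and items 5 and 8 of 3.3 use that term for the earlier randomised drug. Whether it reaches a first start of open-label osimertinib is arguable.

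**5. Dose modification.**

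| Section | Patients and period | Source named |
|---|---|---|
| 6.3.1 | open-label, no time limit | package instructions |
| 6.9.1 | open-label, no time limit | approved local label |
| 7.3.3 | open-label, after final OS analysis | protocol criteria and approach |

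All three cover open-label patients after the final OS analysis. Cross-references among them on this point: none. Before that analysis 7.3.3 does not apply, so the overlap is confined to the extension period.

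**The case against.** The best reply on item 6 is that no site would read lung toxicity as a requirement for treatment. The wording visibly comes from an exclusion list, 3.3 already mixes inclusion and exclusion items, and if 3.2 still applies then exclusion 9 supplies the missing sense. The other places that treat ILD as exclusionary are also less independent than they look: SAP Table 2 restates 3.2, and 1.5, 3.2 and Table 2 all concern study entry. This stands as an argument about likely intent and limits the practical risk. It does not make the text correct, and it works fully only if 3.2 is re-applied at open-label start, which the documents leave unsettled.

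A reader might infer that 3.10 flatly forbids open-label osimertinib after ILD, so that item 6 breaches it outright. The documents do not support that, given how they use *study treatment*. A reader might equally infer that nothing protects a patient whose ILD arose after randomisation. That also goes too far, because items 3 and 8 and section 6.9.6 offer partial cover.

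On dosing, 6.9.1 is itself part of the protocol and contains its label sentence for open-label patients, so the reference in 7.3.3 to protocol criteria can be read as leading back to the label. Section 7.3.3 also leaves room for investigator judgement. That reading is possible, but the text does not state it. The point is therefore kept as secondary.

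**Conclusion.** The main point holds with high confidence. Item 6, one of eight criteria, says as worded the opposite of what its source in 3.2 says. It is most likely a drafting slip, in a safety criterion that sites must apply, and it should be fixed. This conclusion does not depend on which reading of 3.2 is adopted; only the form of the problem changes.

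The dose-modification point holds with lower confidence: three sections, two kinds of source and no cross-reference, for open-label patients after the final OS analysis. A reader might infer that patients would be dosed differently under label and protocol. The label is not in the documents, so no difference in content is shown and none is claimed.

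The documents do not give the number of patients considered for open-label treatment, so no count of affected patients is possible. The 3.9% and 0.4% in 1.5 come from Phase I-III studies of the drug; they are context and not an estimate for this group. Nothing here suggests that any patient was wrongly treated. There is no effect on alpha, power or any formal test.

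**What to change.** Reconcile the wording of 3.3 item 6 with its lead-in and with exclusion 9 in 3.2. State whether 3.2 is applied again at open-label start, and make clear how item 6 relates to 3.10 and 6.9.6.

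Reconcile 6.3.1, 6.9.1 and 7.3.3, or cross-refer them, so that a site can see which source governs dose modification in the extension.

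Which rule holds in each case is for the clinical team. The cost is protocol wording and a letter to sites, with no new procedures or data.

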3.4 Subject enrolment and randomisation

Investigators should keep a record in the screening log of patients who entered the screening.

The Investigators will:

1. Obtain signed informed consent for Screening Part I from the potential patient before mandatory tumour sample is sent to central laboratory for *EGFR* testing.
2. Obtain a unique enrolment number ( code) through the Interactive Voice Response System (IVRS)/Interactive Web Response System (IWRS).
3. Obtain main informed consent before any study specific procedures other than EGFR testing are performed.
4. Determine patient eligibility. See Section 3.

At randomisation Visit, once the patient is confirmed to be eligible, the Principal Investigator or suitably trained delegate will:

5. Obtain a unique randomisation number via IVRS/IWRS.

If a patient withdraws from participation in the study, then his/her enrolment/randomisation code cannot be reused.

Note: Section 4.1 describes the procedures to be carried out during Screening period.

3.5 Procedures for handling incorrectly enrolled or randomised subjects

Subjects who fail to meet the eligibility criteria should not, under any circumstances, be enrolled or receive study medication. There can be no exceptions to this rule.

Where a subject does not meet one or more eligibility criteria but is randomised in error, or is incorrectly started on treatment, the Investigator should inform the study physician immediately, and a discussion should occur between the study physician and the investigator regarding whether to continue or discontinue the patient from study treatment. The study physician must ensure all decisions are appropriately documented.

3.6 Methods for assigning treatment groups

Eligible patients will be centrally randomised to receive either 80 mg AZD9291 orally once daily or matching placebo in a 1:1 ratio using the IVRS/IWRS system.

Patients will be stratified at randomisation based on:

- Stage (IB vs II vs IIIA)
- EGFR mutation (Ex19Del or L858R) In the rare event that a patient has both of these sensitizing mutations, they should be stratified to Ex19Del
- Race (Asian/Non-Asian)

3.7 Methods for ensuring blinding

Investigational product (IP, also referred to as ‘study drug’ in this protocol) will be labelled using a unique material pack code, which is linked to the randomisation code. The IVRS/IWRS will assign the bottles of study material to be dispensed to each patient. This is a double-blind study wherein each patient will receive either the active drug or matching placebo. The active drug and placebo tablets will be identical and presented in the same packaging to ensure blinding of the medication.

3.8 Methods for unblinding

Individual treatment codes, indicating the treatment randomisation for each randomised patient, will be available to the investigators from the IVRS/IWRS. Routine procedures for this will be described in the IVRS/IWRS user manual that will be provided to each site.

The treatment code should not be broken except in medical emergencies when the appropriate management of the patient requires knowledge of the treatment randomisation. Additionally, at the request of the Investigator, following disease recurrence the patient can be unblinded to their treatment allocation to guide future anti-cancer therapy. In both cases, the Investigator documents and reports the action to AstraZeneca representative, without revealing the treatment given to patient to the AstraZeneca representative. For patients being considered for open-label osimertinib upon recurrence, please see Section 3.3.

AstraZeneca retains the right to break the code for serious adverse events (SAEs) that are unexpected and are suspected to be causally related to an IP and that potentially require expedited reporting to regulatory authorities. Treatment codes will not be broken for the planned analyses of data until all decisions on the evaluability of the data from each individual patient have been made and documented.

